Vanguard Multi-Centre Feasibility Trial to Determine if Buttonhole Versus Step-Ladder Cannulation for Home Hemodialysis is Associated with Reduced Overall Cost

Primary Objectives: To determine the feasibility of 1) randomizing patients to step-ladder versus buttonhole cannulation techniques, and 2) coordinating the multiple Canadian sites that are required for the definitive study.

Secondary Objectives: To determine 1) if buttonhole cannulation, compared to step-ladder cannulation is associated with reduced training time for home hemodialysis patients, 2) if buttonhole cannulation, compared to step-ladder cannulation is associated with reduced overall cost, 3) if buttonhole cannulation, compared to step-ladder cannulation is associated with reduced complications (infection – local and systemic, radiologic/surgical interventions, re-trains for needle insertion difficulties, hematoma formation, aneurysm formation, missed insertions), 4) if buttonhole cannulation, compared to step-ladder cannulation is associated with reduced patient discomfort with needling for intensive home hemodialysis patients, and 5) to describe the overall patient population to help explain recruitment challenges

Background

High Dose Hemodialysis

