Study Design: The proposed 12 month vanguard study will be a randomized controlled trial of patients training for home hemodialysis. The primary outcome for the proposed study is feasibility to recruit to the two different needle cannulation arms and coordination of the study centres. Additionally, demographic data will be retrospectively collected on patients who trained to do home hemodialysis, but were not eligible for the study to help explain recruitment challenges.

Patient Population:

Inclusion Criteria

The following inclusion criteria will be used: 1. Adult patients > 18 years old, 2. Training for home hemodialysis using self cannulation, 3. Returning to train to use an AVF (i.e. went home using a CVC or another access that has failed), 4. Able to give informed

consent, 5. Arteriovenous fistula (patients with segments of grafts that are not at the sites of needle insertion may be included), and 6. Life expectancy of greater than 12 months

Exclusion Criteria

The following exclusion criteria will be used: 1. Potential to be lost from the program within 12 months of training (planned living donor transplant, transfer to PD or move from training centre catchment area), 2. Short segments or aneurysms within the AVF that the attending nephrologist believes require buttonhole cannulation, 3. Mechanical heart valves, 4. Patients who require intradermal lidocaine for needle insertion

Study Overview

After obtaining informed consent, basic demographic data will be collected including age, sex, cause of end stage renal disease, arteriovenous access history [date of creation, previous interventions (angioplasties, surgical revisions), previous infections] and comorbidity information to calculate the Charlson comorbidity index. Demographic data will also be retrospectively collected on patients who were training for home hemodialysis but were not eligible to participate in the study.

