Any additional days of training and any days required for re-training will be included in the overall cost. Any differences in the cost of the blunt versus sharp needles and the mupirocin for buttonhole cannulation will be included in the overall cost. Treatment for infection including antibiotics and hospitalizations will be included and costed according to established principles. Similarly, the cost associated with any required angiogram (leading to an angioplasty), angioplasty or surgical revision will be included.

Visual Analogue Scale – Pain with Needling (Appendix 1)

All patients will continue (or start) with the step ladder insertion technique for the first 2 to 3 days at which time they will use the validated 10 cm visual analogue scale to rate the pain they experience with needle insertion. The visual analogue scale will be repeated at 2 additional time points – at the end of training and approximately 2 months after graduating home hemodialysis training. As many of the programs train 3 days per week, the additional time point is to capture the potential differences in perceived needling pain with increased frequency of needle insertion. It is unclear if buttonholes are easier to maintain when used more than 3 days per week as this may be associated with less pain on needle insertion. Topical anesthetics will not be withheld during assessments of pain with the visual analogue scale but the requirement for use will be documented.

Sample Size Calculation

There are a limited number of patients who start home HD each year in Canada. If we are unable to get at least 70% enrollment in the pilot study – it is very unlikely that we will be able to successfully undertake a study with a larger sample size. For the purposes of the feasibility pilot, the first 2 centres (Ottawa and University Health Network) will recruit participants for 18 months with the remaining centre's participating for 12 months. All patients who are eligible for the study will be approached for recruitment. Our goal is to demonstrate that we can successfully recruit. For the definitive study to explore the differences in training time between the two needle cannulation techniques: The mean number of training days for patients with an AVF in the FHN studies was 27.7 with a standard deviation of 10.4 (20). This was reduced by 5 days for patients using a central venous catheter. Assuming that a buttonhole cannulation would

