have a similar impact on training time, 69 patients per groups would give us 80% power to detect this difference. The number required in the trial increases to 107 if the difference is 4 days.

Analysis

For the purposes of the pilot study, basic demographic characteristics of the included and excluded patients will be described using appropriate descriptive statistics. This data will be retrospectively collected on patients who were not enrolled in the study. The percent of qualified patients enrolled in the study for the pilot study to be successful will be $\geq 70\%$. The secondary outcomes will be analyzed on an intent to treat basis upon completion of the main study assuming that this trial is feasible. The comparison of mean training times will be done with an un-paired t-test. A linear regression analysis will also be undertaken to examine predictors of training time including age, sex and Charlson comorbidity score in addition to needle insertion technique. Any differences in pain scores depending of frequency of cannulation will be explored within cannulation techniques. If no differences exist by frequency of cannulation, the data will be combined and the median pain scores will be assessed with a Wilcoxon rank sum test. The different types of complications and costs will be categorized and the overall mean differences will be assessed with an unpaired t-test. Any differences in outcomes by frequency of cannulation will also be explored within each of the secondary outcomes.

For patients who return to train on cannulation technique (started home HD with a CVC or other access that failed); their data will not be included in overall training time but all other study outcomes will be tracked and included in the analysis infections and complications.

The retrospectively collected demographic data will be analyzed in order to describe the patient population.

Data Safety Monitoring Board

Drs. [name] and [name] in addition to [name] (vascular access coordinator) have agreed to monitor the outcomes of this study. If we detect infection rates that are comparable to or greater to the benchmark for central venous catheters as adopted by the Ottawa Hospital - the study will be stopped (external benchmark bacteremia rate of 4.6 per 100 patient months, Nephrology News and Issues 2005, 37-43)

Study Investigators

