The definitive study will be part of the Canadian Intensive Hemodialysis Physician Group with representation from across Canada. The vanguard study will be collecting information from sites in Ottawa ([name]), Toronto (Drs. [name], [name] and [name]), Calgary ([name]) and Vancouver ([name]). All investigators have experience in high dose hemodialysis and clinical investigation. [name] has additional experience in economic analysis and [name] has just published a study of buttonhole versus stepladder cannulation in the in-centre conventional hemodialysis population. All

together, these sites train approximately 70 patients for high dose hemodialysis per year which will provide an adequate number of participants to ensure the success of this pilot study within the 2 years allotted for this grant. If no changes to the protocol are required, feasibility clearly established and sample size achievable, the pilot study data will be retained for the definitive trial.

Appendix 2

References:

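### Recurrent complications are compared by t-test with no time-at-risk term while per-patient follow-up is left unfixed; comparing events per patient-time is a cheap improvement

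*Combined protocol and SAP*

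**What the plan says.** The Analysis section states: "The different types of complications and costs will be categorized and the overall mean differences will be assessed with an unpaired t-test". The Secondary Objectives list the complications as infections, radiologic or surgical interventions, and "re-trains for needle insertion difficulties, hematoma formation, aneurysm formation, missed insertions". Apart from aneurysms, which are assessed at the start and end of the study, these can recur in the same patient.

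The length of observation has to be inferred:

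- Study Design: "The proposed 12 month vanguard study will be a randomized controlled trial".
- Inclusion Criteria: "Life expectancy of greater than 12 months".
- Exclusion Criteria: "Potential to be lost from the program within 12 months of training".
- Sample Size Calculation: the first two centres "will recruit participants for 18 months with the remaining" centres taking part for 12 months.
- Study Investigators: enough patients are expected "to ensure the success of this pilot study within the 2 years allotted for this grant".

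None of these sets a start and end of follow-up for a patient. The cost section lists components, for example "Any additional days of training and any days required for re-training will be included in the overall cost", without a time horizon. The Analysis section defers the secondary outcomes, by intent to treat, to completion of the main study.

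Patient-time does appear elsewhere. The Study Overview names infection rates as a purpose given to patients and staff, and the Data Safety Monitoring Board section uses a bacteremia benchmark of 4.6 per 100 patient-months.

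**The concern.** Hematomas, missed sticks, infections, interventions and re-trains accumulate with time at risk. If all patients are followed equally long, a difference in mean counts is a difference in rates times a constant, and nothing is lost. If follow-up varies, part of the spread in counts reflects only how long each patient was watched, and a t-test on totals treats that as noise. If follow-up is shorter in one arm, that arm shows fewer events even when the true rates are equal.

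The exclusion criteria remove only foreseeable loss (planned living donor transplant, transfer to PD, a move). Death, an unplanned transplant or access failure can still end follow-up early under a 12-month plan. These outcomes carry the harm side of the comparison. The Analysis section plans no between-arm rate to set beside the infection-rate purpose or the patient-month benchmark.

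**Working it through.** **1. The plan's own figure.** Inputs from Sample Size Calculation: SD 10.4 days, difference 5 (or 4) days, power 80%. Alpha is not stated; two-sided 5% is assumed.

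n per group = 2(1.960 + 0.842)² × SD²/Δ²

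- Δ = 5: 2 × 7.85 × 108.16/25 ≈ 67.9. The t-based solution is 68.9, so 69.
- Δ = 4: 2 × 7.85 × 108.16/16 ≈ 106.1. The t-based solution is 107.1, and power at 107 is 80.0%.

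Both stated figures reproduce. They concern training time; no power is stated for complications. I use 69 per arm below.

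**2. How unequal could follow-up be?** If data collection at the first two centres closed with the 24-month grant, the last patient there would have 24 − 18 = 6 months and the first 24. With even accrual, those entering in months 12 to 18, or 6/18 = one third, could not reach 12 months. This is a scenario; no section says that collection closes then. The other scenario is an intended 12 months with 20% early loss.

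**3. Why frequency matters.** Let m be the mean count, φ the squared between-patient CV of the event rate, and c² the squared CV of follow-up time.

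Var(count) = m + φm²(1 + c²) + m²c²; with fixed follow-up it is m + φm².

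For follow-up uniform over 6–24 months, the mean is 15 and c² = (18²/12)/15² = 0.12. With CV 0.8, φ = 0.64.

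- 0.5 events/month, m = 7.5: (7.5 + 40.32 + 6.75)/(7.5 + 36) = 54.57/43.5 = 1.25.
- Bacteremia at the Background's upper rate, 0.60 per 1000 patient-days = 0.0183/month, m = 0.27: the ratio is about 1.05.

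So variance grows materially only for frequent events.

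**4. Power, frequent events.** Simulated gamma-Poisson counts, 69 per arm, with assumed 0.5/month, CV 0.8 and rate ratio 1.5. The rate model is Poisson with a log-exposure offset and robust errors, at nominal 5%.

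| Follow-up | t-test on totals | Rate model |
|---|---|---|
| Common 12 months | about 75% | 77% |
| 12 months, 20% early loss | 69% | 74% |
| 6–24 months | 67% | 75% |

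The robust test runs slightly above nominal size (5–6%). With both tests calibrated to 5%, the figures are 77% vs 77% at a common 12 months and 67% vs 73% at 6–24 months. A t-test on per-patient rates reaches 76% at 6–24 months.

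Sensitivity at 6–24 months, calibrated: the loss is 1–6 points over 0.1–1.0 events/month and CV 0.5–1.2. It is 60% vs 79% at 0.5/month with CV 0.3 and rate ratio 1.25.

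**5. Follow-up differing by arm, equal true rates** (0.5/month, CV 0.8, 6–24 months).

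- Exposure 10/20/30% shorter in one arm, unrelated to risk: the t-test on totals rejects 9/25/53%; the rate model about 6%.
- Highest-risk 20% of one arm leave halfway: the t-test rejects 35% and the rate model 18%. The mean-count ratio is 0.77 and the rate ratio 0.86, against a truth of 1.0. The offset reduces this bias but does not remove it.

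**6. Bacteremia.** The Background's 0.15 to 0.60 per 1000 patient-days equals 0.46 to 1.83 per 100 patient-months. Power for assumed rate ratios 3/5/10, 6–24 months:

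- At 0.60: t-test 66/88/97%, exact rate test 65/87/97%.
- At 0.15: 20/32/44% vs 11/19/25%. This is not like for like: the exact test's null size there is about 2.5–3%, against about 5% for the t-test.

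**7. Costs.** Training days fall mostly at the start, while needles and mupirocin recur. The arm difference is roughly A + B × h for horizon h, so it depends on h even with equal follow-up. The mean difference is still the right target.

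**The case against.** The strongest reply is that the t-test is not itself at fault. The Analysis wording does not say raw totals, so a t-test on per-patient rates is not excluded, and at 6–24 months it performs about as well as the rate model. That stands: what is missing is the denominator and the follow-up definition, not a particular model.

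Second, Study Design and the eligibility criteria point to 12 months, where the loss vanishes. That stands for complete follow-up. It does not cover unforeseen exits.

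Third, a reader might infer from 18 + 12 = 30 months, against a 24-month grant, that the documents contradict themselves or that follow-up will run from 6 to 24 months. They do not support this. The 2-year limit concerns success of the pilot, whose criterion is enrolment. The complication comparisons wait for the main study, whose timetable is not given, and the 18-month window covers two centres only.

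Fourth, a reader might infer that the trial will produce no rate at all. The stopping rule already needs a bacteremia rate in patient-months; the gap is confined to the between-arm comparison in the Analysis section.

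**Conclusion.** The point holds in a limited form: a cheap improvement. The plan gives recurrent complications no time-at-risk term and does not fix follow-up. With complete, equal follow-up this costs essentially nothing. With unequal follow-up, a t-test on totals loses about 5 to 8 points of power for frequent events under the stated assumptions; part of that gap is the rate model's slightly liberal size, and other assumed rates and CVs give smaller or larger losses. The event rate, CV, rate ratio and follow-up patterns are not from the documents.

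Two stronger conclusions are not supported. The documents do not show that follow-up will differ by arm, so bias is a possibility to guard against and not a finding. Nor does the plan sacrifice power for bacteremia; the gain there is an interpretable rate. The missing cost horizon and the undefined interval between aneurysm assessments are mainly missing detail.

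The feasibility endpoint is unaffected, the comparisons are deferred to the main study, and retention of pilot data is conditional.

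**What to change.** - Define each patient's start and end of follow-up, and record exit dates and reasons.
- Compare infections, hematomas, missed sticks, interventions and re-trains as events per patient-time, by intent to treat. Use negative-binomial or robust Poisson regression with a log-exposure offset, or a t-test on per-patient rates stated as such. The latter gives very short follow-up the same weight as long follow-up.
- Report bacteremia as a rate ratio with an interval, noting that an exact test is conservative when events are few.
- Report exits by arm and reason, and state that an offset does not remove bias when exit is related to event risk.
- Keep the mean difference for costs, over a stated common horizon. Fix the time of the closing aneurysm assessment.

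The cost is a few sentences in the Analysis section and exit fields on the case report form, which the Study Overview says is still to be developed and pilot tested. The stopping rule already requires patient-months. The downsides are slightly more analysis work and a robust rate test slightly above nominal size (5–6%).

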The insertion of needles into an AVF has traditionally been via the step ladder or continuous site rotation technique. However, the buttonhole method was introduced in the 1970's in an attempt to address some of the challenging issues associated with AVF accesses.¹⁹ In the buttonhole technique, a constant site is used for needle placement that ultimately results in a fibrous tract. Once the tract has formed blunt needles can be used instead of sharp needles for each treatment. The presence of a tract may simplify the needle insertion technique and lead to enhanced patient confidence with needle placement. Although no studies have reported training times in association with needle insertion technique, Pipkin et al have demonstrated a mean reduction in training time for home hemodialysis patients of 5 days when a central venous catheter was used for an access compared to an AVF.²⁰ It is reasonable to assume that well established buttonholes may also lead to a similar reduction in training times. Other reported benefits of buttonhole cannulation include less painful needling,²¹⁻²⁴ fewer needle infiltrations,^{19,24,25} fewer interventions²⁶ and a reduction in aneurysm size.²³ While earlier studies demonstrated a reduction in pain with buttonhole needling, more recent studies show either no reduction in pain,^{27,28} or even an increase in pain.²⁶ However, the effect of frequency of use on the maintenance of the buttonhole and the perception of pain has not been explored. Importantly however, there has also been increasing concern about the potential for an increased risk of infection using the buttonhole cannulation technique with estimates of *Staphylococcus aureus* (*S. aureus*) bacteremia for patients receiving high dose dialysis between 0.15 to 0.60 episodes per 1000 patient-days across 4 studies.²⁹⁻³² In an indirect comparison between high dose home hemodialysis with buttonhole cannulation versus in-centre conventional hemodialysis with rope-ladder cannulation, the relative risk for bacteremia ranged between 30 to 120. Importantly, *S. aureus* bacteremia was associated with devastating consequences, including septic arthritis, septic pulmonary emboli, vertebral osteomyelitis, and death in a single centre's experience.³³ In one small study, the risk of infection associated with buttonhole

cannulation was prevented by the application of topical mupirocin at the buttonhole sites post hemodialysis.

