Differences between Conventional In-Centre and Home Hemodialysis

Although ease of cannulation is important in-centre, it is even more important for patients at home. It is unclear if the potential ease of use of buttonhole cannulation might lead to enhanced home hemodialysis recruitment rates and reduced training time. The ease of use of CVCs likely contributed to the decreased training time that was required for patients with this type of access in the Frequent Hemodialysis Network Trial. There is emerging controversy about reduced pain on needle insertion with buttonhole cannulation in centre. However, it is unclear if using the buttonholes more frequently might result in reduced cannulation pain secondary to 'enhanced' maintenance of the fibrous tract. Lastly, for patients who are treated in-centre, needles are typically inserted by skilled allied health team members. At home, needles are inserted by the patient or a family member helper who must be trained to perform home hemodialysis. It is unclear if allied health team members are more likely to follow strict rules for cleanliness compared to patients at home such that infection risks might be less in-centre. Also, the enhanced frequency of use of the buttonholes for high dose hemodialysis might be associated with an increased risk of infection.

Summary and Conclusions

There is increasing interest in high dose home hemodialysis therapies. Although both needle cannulation techniques have been used for home hemodialysis, the relative benefits and risks of the two techniques have never been explored in a randomized controlled trial. The potential advantages of buttonhole cannulation for this patient population may be enhanced recruitment, reduced training time, reduced aneurysm formation and a reduced number of interventions. The reduction in training time may result in significant savings to the hospitals in which reimbursed training days are fixed. The benefits may be offset by the potential for an increased risk of infection. However, the potential benefits and risks of buttonhole cannulation versus step-ladder cannulation remain speculative as they have not been studied in a rigorous prospective trial of home hemodialysis patients treated with high dose hemodialysis.

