The home hemodialysis run sheet will be modified so that the patient can record any instances of hematoma formation (obvious bruising at the arteriovenous site that occurs at the time of needle insertion or withdrawal) or missed needle sticks (unable to use the needle for dialysis). For buttonhole cannulation, the need to use a sharp needle instead of the usual blunt needle will be considered a missed needle stick even if a separate needle insertion site is not required. Patients will be instructed to come to the home dialysis unit if they notice any localized signs of infection over the AVF including heat, erythema, purulent drainage or induration. A swab will be sent for gram stain, culture and sensitivity; infection will be diagnosed if neutrophils are present with cultured bacteria. Additionally patients will be asked to contact the unit and present themselves to the nearest emergency department if they develop fever, chills and/or hypotension with the hemodialysis treatment. An access related bacteremia will be defined using CDC criteria

(at least one of the following: 1) Patient has a recognized pathogen cultured from one or more blood cultures and the pathogen is not related to an infection at another site or 2) patient has fever, chills, and/or hypotension as well as positive laboratory cultures from two or more blood samples drawn on separate occasions which are not related to infection at another site and do not reflect contamination). As the most common pathogen is *S. aureus*, all patients with *S. aureus* related bacteremia will be monitored for metastatic complications including an echocardiogram at the discretion of the treatment center. Access interventions including angioplasties and surgical revisions will be documented. The vascular access coordinator, or similarly trained individual, will document the presence of aneurysms at the start and completion of the study. A standardized tool for assessment of the number of aneurysms, size and potential risk of rupture (thinness of skin) will be developed with the assistance of skilled vascular access coordinators (access documentation tool).

Costs of Vascular Access

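### The complication analysis leaves *overall* undefined and commits to no separate bacteremia comparison; if the types are pooled, frequent needling events dilute an infection harm

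*Combined protocol and SAP*

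**What the plan says.** Secondary objective 3 asks whether buttonhole "is associated with reduced complications", and lists the components as "infection – local and systemic, radiologic/surgical interventions, re-trains for needle insertion difficulties, hematoma formation, aneurysm formation, missed insertions". It gives no weights and no order of importance.

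The Analysis section has one sentence on how these are compared: "The different types of complications and costs will be categorized and the overall mean differences will be assessed with an unpaired t-test". *Overall* is not defined there or elsewhere. No rate model, exact method or separate test is named for bacteremia.

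The background expects the components to move in different directions. The section on buttonhole versus stepladder cannulation cites reports of fewer infiltrations and interventions. It also gives *S. aureus* bacteremia rates "between 0.15 to 0.60 episodes per 1000 patient-days across 4 studies" and says of an indirect comparison that "the relative risk for bacteremia ranged between 30 to 120". Summary and Conclusions adds: "The benefits may be offset by the potential for an increased risk of infection".

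**The concern.** A simple total gives a bruise or a failed needle the same weight as a bloodstream infection. Missed sticks can occur at every session, while bacteremia at the quoted rates occurs at most about once in four to five patient-years. Noise in the common events can therefore bury a large relative increase in the rare one, and a fall in the common events can offset it.

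Infection is the main harm that the protocol itself names. Because the rule is open, the choice between a total and separate comparisons could also be made after the results are known, in a trial whose intervention cannot be blinded.

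**Working it through.** **1. The plan's own figure.** Sample Size Calculation gives 69 per group for a 5-day difference in training time, SD 10.4, 80% power. With two-sided alpha 0.05 (assumed; not stated), n = 2(1.96 + 0.84)² × (10.4/5)² ≈ 68, and the t-distribution version gives 68.9, so 69 is reproduced. It concerns training time; the plan gives no sample size for complications. I use 69 per arm and assume one year of follow-up each, since follow-up per patient is not stated.

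**2. Bacteremia with buttonhole.** 0.15 × 365.25/1000 = 0.055 per patient-year; 0.60 × 365.25/1000 = 0.219. In 69 patient-years that is 3.8 to 15.1 expected episodes.

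**3. Bacteremia with step-ladder.** No home step-ladder rate is given. Dividing by the quoted relative risks, 0.60/120 = 0.15/30 = 0.005 per 1000 patient-days, or 0.0018 per patient-year (0.13 expected episodes in 69 patient-years). The pairing is my assumption, and the quoted comparison is with in-centre conventional dialysis.

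**4. Missed sticks.** No rate is given. Assume 5 double-needle sessions a week, 5 × 52 × 2 = 520 insertions a year, of which 1% are missed: 5.2 per patient-year. Over 3 to 5 sessions a week and 1% to 5% missed, the range is 3.1 to 26.

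**5. Share of a pooled count (these two components only).** At 5.2 missed sticks: 0.055/5.255 = 1.0% and 0.219/5.419 = 4.0%. Over the wider range, with buttonhole misses 20% lower: 0.055/(0.055 + 20.8) = 0.3% to 0.219/(0.219 + 2.5) = 8.1%. Other types would lower the share further.

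**6. Pooled t-test, simulated.** 69 per arm, one year, bacteremia 0.219 against 0.0018 per year, step-ladder misses 5.2 per year, negative-binomial counts. Percentage of trials in which the pooled mean is significantly higher with buttonhole:

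| Buttonhole misses | Dispersion 1 | Dispersion 0.25 |
|---|---|---|
| 10% fewer | 1% | 1% |
| Equal | 4% | 5.5% |
| 10% more | 11% | 22% |

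With no true difference of any kind, the figure is about 2.5%. The last row mainly reflects needling, not infection.

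**7. Bacteremia alone, exact conditional test.** 15.1 against 0.13 expected episodes: power over 99%. With relative risk 30 at the same rate, about 98% to 99%. At the lowest rate, 3.8 against 0.13: about 16% to 17%.

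**8. What zero events would show.** The exact 95% upper limit for 0 episodes in 69 patient-years is 3.69/69 = 0.0535 per year, or 0.146 per 1000 patient-days. That is about the lowest buttonhole rate quoted, 0.15.

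**The case against.** A reader might infer that complications will be collapsed into a single number. The documents do not establish this. The Analysis sentence speaks of categorizing and of differences in the plural, which fits one comparison per type. The same section mentions infections apart from complications, Study Overview does likewise, and AVF Access Complications gives infection its own definitions. Aneurysms are to be assessed by number, size and rupture risk, which do not add naturally to event counts. This stands: pooling is a natural reading, not a fact. But the plural also fits one complication total and one cost total, and none of these places states an analysis rule for infection.

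A reader might also infer that the trial would probably report fewer complications with buttonhole while infections rise. That is not supported. With 10% fewer misses, the pooled test significantly favours buttonhole in only about 5% of trials, against about 2.5% by chance, and the 10% comes from no document. Under AVF Access Complications, a change from blunt to sharp needle in the buttonhole arm "will be considered a missed needle stick even if a separate needle insertion site is not required", which works against such a gain. The problem that remains is dilution: even with equal misses the pooled test seldom shows the harm.

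Bacteremia is also watched separately by the monitoring board. Its benchmark of 4.6 per 100 patient-months is 46/30.44 = 1.51 per 1000 patient-days, or 2.5 to 10 times the quoted buttonhole rates. A harm of the quoted size would not be expected to reach it, so it does not replace a comparison between arms.

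Finally, the top rate need not apply: the protocol specifies an antimicrobial cream at buttonhole sites and cites one small study in which infection was prevented. That is why the low-rate result is shown beside the high one.

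**Conclusion.** The concern holds as a gap in specification. The plan permits a pooled complication total, does not define *overall*, and commits to no separate bacteremia comparison. Under pooling at the highest quoted rate, harm is shown in about 1% to 22% of trials depending on the direction of missed sticks, against over 99% for bacteremia alone. These figures rest on an assumed missed-stick rate, session frequency, dispersion and one-year follow-up, and on an indirect relative risk.

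Separating the types does not by itself make the trial informative on infection: at the lowest quoted rate, 69 per arm has only about 16% to 17% power. If the per-type reading was intended, an unpaired t-test still suits bacteremia poorly, because nearly all patients would have a count of zero.

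The matter is secondary for the vanguard phase, whose primary outcome is feasibility. The secondary outcomes are to be analysed on completion of the main study, so the rule can be settled before then.

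**What to change.** In the Analysis section:

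- State that each complication type listed in secondary objective 3 is compared separately between arms.
- Name access-related infection (bacteremia and local infection) as the main harm comparison, reported as events and patient-time by arm with an exact 95% interval instead of a t-test on means.
- Treat any pooled count as supportive only, not as the answer to objective 3.
- State that a non-significant infection result will not be read as evidence of safety, and give the zero-event limit above as the reason.

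The cost is some wording and several tables in place of one, and there will be no single complication summary. No new data are needed, because infections are already defined and recorded separately.
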